2.1.2. Secondary Objectives

The secondary objectives are:

- To assess systemic exposure to trifarotene and its major metabolites after topical application of the investigational product (IP) on up to 90% body surface area (BSA) twice weekly.
- To assess safety for up to 180 days of dosing with open-label trifarotene cream HE1 200 µg/g.

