3.5. Method of Assigning Subjects to Treatment Groups

Subjects will be randomized in a 1:1:1 ratio to trifarotene cream HE1 100 µg/g or 200 µg/g or vehicle cream in the Double-blind Period.

Subjects who continue into the OLE will receive trifarotene cream HE1 200 µg/g and apply the same fixed dose in the same manner as in the Double-blind Period for an additional 90 days.

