- **Intent-to-treat (ITT):** all randomized subjects. This population will be used as the primary population for the analysis of efficacy for the Double-blind Period of the study. Subjects will be analyzed by randomized treatment.
- **Modified intent-to-treat (mITT):** all subjects in the Safety population with at least 1 postbaseline assessment of efficacy in the Double-blind Period. Subjects will be analyzed by randomized treatment.
- **Per-protocol (PP):** subjects in the mITT population who met all inclusion criteria and no exclusion criteria, were compliant with study drug application, and who had no significant protocol deviations. Subjects will be analyzed by actual treatment received.
- **Pharmacokinetic (PK):** all subjects in the Safety population who have at least 1 plasma sample with quantifiable concentration. This population will be used to summarize all PK endpoints. Subjects will be analyzed by actual treatment received.

The following analysis populations are planned for the OLE of this study:

- **OLE Safety:** all subjects who complete the 90-day Double-blind Treatment Period and receive at least 1 application of study drug in the OLE.
- **OLE ITT:** all subjects who complete the 90-day Double-blind Treatment Period and sign the OLE informed consent.
- **OLE mITT:** all subjects in the OLE Safety population with at least 1 assessment of efficacy after Visit 6.
- **OLE PP:** all subjects in the OLE mITT population who met all inclusion criteria and no exclusion criteria, were compliant with study drug application from baseline through EOT, and who had no significant protocol deviations throughout the study.

Since all subjects in the OLE are to receive trifarotene cream HE1 200 µg/g, analyses will be by actual treatment received.

Inclusion in the analysis populations will be determined prior to database lock. Deviations related to COVID-19 will also be evaluated in determining PP population eligibility.

6. General Issues for Statistical Analysis

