6.1. Statistical Definitions and Algorithms

6.1.1. Baseline

The last nonmissing assessment recorded prior to the first dose of treatment in the Double-blind Period will be used as the baseline observation for all calculations of change from baseline, including those in the OLE.

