The change from baseline IGA score will be analyzed using a mixed model for repeated measures (MMRM). The MMRM model will include change from baseline in IGA score as the dependent variable, treatment, study visit, treatment-by-visit interaction, and age group as fixed effects, subject as a random effect, and baseline IGA score as a covariate. All post-baseline study visits will be included in the model; however, the primary comparison will be between the active trifarotene cream HE1 groups and vehicle at Day 90. An unstructured covariance matrix will be used to model the within-subject errors. The Kenward-Roger approximation will be used to estimate degrees of freedom. In case of convergence issues, other covariance structures will be explored including autoregressive (AR(1)), compound symmetry (CS), and variance components (VC) with each model fit to find the covariance structure with the best fit. The fit statistics will be compared for all covariance structures; the structure with the smallest Akaike information criterion will be retained as the preferred model and noted in the resulting table. For the OLE period, the model will not include treatment or treatment-by-visit interaction since all subjects receive the same treatment in the OLE.

The least squares (LS) mean change from baseline will be presented along with the associated 95% CI within each treatment group. The overall *P* value of the model will be presented to test

the null hypothesis that the change from baseline to subsequent study visit is 0 with a 2-sided alternative considering a difference in either direction.

In comparing treatments (active trifarotene cream HE1 groups minus vehicle), LS mean differences in change from baseline will be presented along with associated 95% CIs and *P* values. The null hypothesis that the difference in change from baseline in active trifarotene cream HE1 groups minus control vehicle is 0 with a 2-sided alternative considering a difference in either direction. Even if a difference from vehicle is observed, as described above, successful treatment is defined as clear/almost clear overall (IGA scores of 0 or 1) and at least a 2-grade change from baseline.

The observed value and change from baseline in IGA score will also be summarized descriptively by study visit and treatment group using descriptive statistics in addition to the above noted models for the Double-blind Period and OLE. Categorical IGA scores will also be presented.

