Subjects with a TEAE Leading to Discontinuation of Study Drug	XX (XX.X%)	XX (XX.X%)	XX (XX.X%)	XX (XX.X%)	XX (XX.X%)
Subjects with an AE leading to Death	XX (XX.X%)	XX (XX.X%)	XX (XX.X%)	XX (XX.X%)	XX (XX.X%)

Abbreviations: AE = adverse event; CRF = case report form; MedDRA = Medical Dictionary for Regulatory Activities; SAE = serious adverse event; TEAE = treatment emergent adverse event.

Note: Percentages are n/Number of subjects in the Safety Population within actual treatment group and overall*100. AEs were coded using MedDRA version 21.1. A TEAE is any AE with an onset at the time of or following the start of treatment with study drug through the Follow-up Visit or Early Termination Visit, whichever occurs first. This will include any AE starting prior to the start of treatment but increasing in severity or relationship at the time of, or following, the start of treatment with study drug through the Follow-up Visit or Early Termination Visit, whichever occurs first.

[1] Subjects are counted only once at the worst severity. If a severity designation is missing, it will be considered as severe.

[2] Subjects are counted only once at the strongest possible relationship. If a relationship designation is missing, the AE will be considered as related. This relationship is categorized for summarization as follows: Related = Related and Possibly Related; Not Related = Not Related and Unlikely Related.

SOURCE: Listing 16.2.7.1

Table 14.3.1.1.2
Overall Summary of Treatment Emergent Adverse Events during the OLE
OLE Safety Population

Same shell as Table 14.3.1.1.1

Programming note: Only include one set of columns for Trifarotene cream HE1 200 ug/g.

Update Note: to read "Note: Percentages are $n/\text{Number of subjects in the OLE Safety population within treatment group} \times 100$. All subjects received Trifarotene cream HE1 200 ug/g in the OLE." Add OLE = open label extension to Abbreviations.

Table 14.3.1.2.1
Incidence of Treatment Emergent Adverse Events during the Double-blind Period by System Organ Class and Preferred Term
Safety Population

System Organ Class Preferred Term	Trifarotene cream HE1 100 ug/g (N=XX)	Trifarotene cream HE1 200 ug/g (N=XX)	Overall Trifarotene cream HE1 (N=XX)	Vehicle (N=XX)	Overall (N=XX)
Subjects with at least 1 TEAE	XX (XX.X%)	XX (XX.X%)	XX (XX.X%)	XX (XX.X%)	XX (XX.X%)
System Organ Class 1	XX (XX.X%)	XX (XX.X%)	XX (XX.X%)	XX (XX.X%)	XX (XX.X%)
Preferred Term 1	XX (XX.X%)	XX (XX.X%)	XX (XX.X%)	XX (XX.X%)	XX (XX.X%)

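### The open-label summary tables and models pool three exposure histories into one 200 µg/g group, so no planned summary isolates the 180 days of dosing named in the secondary safety objective

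*SAP*

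**What the plan says.** **Design.** SAP Section 3.5: "Subjects will be randomized in a 1:1:1 ratio to trifarotene cream HE1 100 µg/g or 200 µg/g or vehicle cream in the Double-blind Period". It continues: "Subjects who continue into the OLE will receive trifarotene cream HE1 200 µg/g and apply the same fixed dose in the same manner" as before, for a further 90 days.

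**Grouping in the OLE.** Section 5 (Analysis Populations) sets the rule: "Since all subjects in the OLE are to receive trifarotene cream HE1 200 µg/g, analyses will be by actual treatment received". As everyone's actual OLE treatment is the same, this gives one group. Section 9.1.2 tabulates serious adverse events by arm for the double-blind period but only overall for the OLE, and Section 7.4 does the same for compliance. The shell for the overall OLE adverse event summary (Table 14.3.1.1.2) instructs: "Only include one set of columns for Trifarotene cream HE1 200 ug/g". The OLE shells for adverse events by system organ class, laboratory data, vital signs, ECG, IGA, VIIS, roughness, palm/sole, fissures and ectropion also show a single 200 µg/g group.

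**OLE models.** Section 8.1.1: "For the OLE period, the model will not include treatment or treatment-by-visit interaction since all subjects receive the same treatment in the OLE". Sections 8.2.1 to 8.2.3 repeat the rule for VIIS, roughness and palm/sole. Under Section 6.1.1 the last value before the first double-blind dose "will be used as the baseline observation for all calculations of change from baseline, including those in the OLE".

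**Objective.** Section 2.1.2 lists: "To assess safety for up to 180 days of dosing with open-label trifarotene cream HE1 200 µg/g".

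**The concern.** The reason given for dropping treatment is true of current treatment but not of exposure. At Day 104, the first OLE clinic visit, a former vehicle subject has had about 14 days of active drug and a former 200 µg/g subject about 104. At Day 180 the figures are 90 and 180. The planned tables and models average these subjects together.

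For safety, a late or cumulative effect in subjects on 200 µg/g throughout is diluted by the other two groups, and first-exposure reactions in former vehicle subjects can look like part of the long-term profile. The 180-day incidence cannot be rebuilt by adding tables. The double-blind tables are by arm and the OLE tables are pooled, and a subject with events in both periods would be counted twice.

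For efficacy, Section 8 allows one kind of formal inference in the OLE: change from baseline. That baseline precedes the double-blind period, so the P value contains whatever happened in the first 90 days, including the response to vehicle. The SAP itself plans for 40% success on vehicle (Section 3.1). The OLE change from baseline could therefore be significant even if open-label treatment added nothing.

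**Working it through.** **1. The plan's own figure.** Days on 200 µg/g at the end of the OLE = double-blind days on 200 µg/g + 90.

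- 200-to-200: 90 + 90 = 180
- 100-to-200: 0 + 90 = 90 (plus 90 days at 100 µg/g)
- Vehicle-to-200: 0 + 90 = 90

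The 180 days in Section 2.1.2 reproduce as a maximum, and in one of three sequences only. No sequence has 180 *open-label* days, because the OLE lasts 90.

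**2. How many subjects.** Inputs: 1:1:1 allocation (Section 3.5); 65 enrolled before termination (Section 1); planned 120 with 20% drop-out or nonevaluable (Section 3.1). Assumptions: the 65 were all randomized, arms are equal, loss is equal across arms, and everyone not lost enters the OLE. Number with 180 days = (N/3) × (1 − d).

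- N = 65, d = 0.20: 21.7 × 0.8 = 17.3, out of 65 × 0.8 = 52
- N = 65, d = 0: 21.7 out of 65
- N = 65, d = 0.30: 15.2 out of 45.5
- As planned, N = 120, d = 0.20: 32 out of 96

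**3. What a clean safety result would mean.** With zero events in n subjects the one-sided 95% upper limit is 1 − 0.05^(1/n).

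- The 200-to-200 group, n = 17.3: 15.9%
- The pooled group read as 180-day data, n = 52: 5.6%
- Across 0% to 30% loss: 12.9% to 17.9% for 200-to-200, and 4.5% to 6.4% for the pooled group

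**4. What pooling does to a rate.** Two illustrations with assumed OLE event rates, in the order vehicle-to-200, 100-to-200, 200-to-200:

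- First-exposure pattern, 40%, 20%, 10%: pooled (40 + 20 + 10)/3 = 23.3%
- Late-effect pattern, 10%, 10%, 30%: pooled (10 + 10 + 30)/3 = 16.7%

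Neither pooled figure describes any of the three sequences.

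**5. Where the prior arm is kept.** Section 13.5 sorts the listings by treatment, and most listing shells are headed by randomized treatment. The same heading applies to the shell used for OLE withdrawals due to adverse events, OLE serious events and OLE deaths (Tables 14.3.3.1.2 onward), and to the abnormal laboratory listing (Table 14.3.4.1). The adverse event and laboratory listings also give study day from first dose.

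**6. Shells that do not fit the rule.** The OLE local tolerability shell (Table 14.3.6.3.2) and physical examination shell (Table 14.3.6.4.2) reuse multi-arm layouts with no single-column instruction. The OLE concomitant medication shell (Table 14.3.6.5.2) asks for a further column for all trifarotene subjects. Section 5 would still put one group in each.

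**The case against.** **The data are not lost.** A reader might infer that all open-label results are pooled and that the 180-day objective cannot be answered. The SAP does not support that. The listings identify the randomized arm for each serious, fatal or withdrawal event, the first 90 days of the 200 µg/g arm are tabulated separately, and some OLE shells are ambiguous rather than single-column. What is missing is a planned summary. This part of the objection stands, and it limits the point to the summary tables and models. Sequence tables made after unblinding would, however, have to be labelled post hoc under Section 1.

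**The objective is loosely worded.** Up to 180 days is a maximum, and the objective also calls the dosing open-label. If it meant 180 days of trifarotene at any strength, the 100-to-200 sequence would count too: two thirds, or about 35 of 52. Even then the former vehicle subjects are mixed in and no table separates them.

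**The baseline is openly chosen.** The success definition needs the pre-treatment value, and that value is a natural reference for a 180-day change. The listed efficacy endpoints all end at Day 90. The choice is therefore not an error, and the OLE model does not claim to isolate the open-label effect. The limit lies in what its P value can be taken to show.

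**The size can be exaggerated.** At the planning rates of 70%, 70% and 40%, a reader might average to 60% and say that a 30-point gap is hidden on OLE entry. No planned table would show that figure: Day 90 success is given by arm in Table 14.2.1.1.1, and the OLE success table starts at Day 104.

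**Small groups.** Prior arm needs 2 parameters. With five OLE visits, prior arm by visit needs 2 × 4 = 8 more, alongside an unstructured covariance with about 17 subjects per group. That objection stands against making the full interaction model mandatory.

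**Conclusion.** The point holds for the planned OLE summary tables and models. Section 5 makes the OLE one group, and Section 9.1.2 and most OLE shells follow it. About one third of that group has 180 days at 200 µg/g by Day 180 and about two thirds have 90: roughly 17 of 52, with a range of 15 of 46 to 22 of 65. For an event not seen at all, the data on 180-day exposure would support an upper limit of about 16%, not the 6% that the pooled count suggests.

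The OLE models average the same three histories, and their change from baseline includes the double-blind response, so they do not show what open-label treatment added.

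The counts rest on equal arms, equal loss and complete roll-over. Early termination or refusal of OLE consent would lower them. The one-third share depends on balance between arms, not on the overall level of loss.

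**What to change.** - Show the OLE adverse event, serious adverse event, local tolerability and key efficacy tables by randomized double-blind arm (vehicle-to-200, 100-to-200, 200-to-200) plus total. The pooled column stays as the total.
- Add one cumulative Day 1–180 table of treatment-emergent events and local tolerability for the 200-to-200 group, counting each subject once. The current OLE tolerability shell stops at Day 150, although Table 2 schedules the assessment at Day 180.
- Add a descriptive change from Day 90 by prior arm. Put prior arm in the OLE repeated-measures model where it converges, with prior arm by visit optional.
- Reconcile the 180 open-label days in Section 2.1.2 with the 90-day OLE in Section 3.1, and the OLE tolerability, physical examination and concomitant medication shells with Section 5.

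No new data are needed. The cost is some columns, a few added tables and small cells of about 15 to 22 subjects, which should be read descriptively. The changes should be made before unblinding so that the tables count as planned.

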8.1.2. Multiple Imputation

Multiple imputation (MI) of the primary endpoint will be performed as an analysis of sensitivity to missing data in the Double-blind Period only. Following database lock, thorough assessment on the extent of missing data due to COVID-19 will be carried out specifically as pertains to the primary and secondary endpoints. This will inform decisions around reasonability of imputing missing data for secondary endpoints in the Double-blind Period as well. The final determination will be documented in the CSR.

MI assumes that the statistical behavior of drug- and control-treated subjects after discontinuing study drug becomes that of the vehicle group. Multiple-imputations will be used to replace missing IGA outcomes using multiple draws from the posterior predictive distribution estimated from the vehicle treatment group. IGA scores will be imputed and then categorized as treatment success according to Section 8.1.1 above. A placebo-based pattern mixture model (PMM) will be utilized following the steps outlined in Ratitch B and O’Kelly, M.J. (2011)⁴.

Data are processed sequentially by repeatedly calling SAS[®] PROC MI to impute missing outcomes at study visit $t = 1, \dots, T$. The following procedure is followed:

- *Initialization (Step 1)*. Set $t = 0$ (baseline study visit).
- *Iteration (Step 2)*. Set $t = t + 1$. Create a dataset combined records from drug- and vehicle-treated subjects with columns for covariates **X** and outcomes at study visits 1, ..., t with outcomes for all subjects set to missing at study visit t and set to observed or imputed values at study visits 1, ..., $t-1$.
- *Imputation (Step 3)*. Run placebo-based pattern mixture model in SAS[®] PROC MI on this data to impute missing values for study visit t using previous outcomes for study visit 1 to $t-1$ and baseline covariates.
 - Replace imputed data for all subjects at study visit t with their observed values, whenever available. If $t < T$ then go to Step 2, otherwise proceed to Step 4.
 - Repeat steps 1-3, m times with different seed values to create m imputed complete datasets. In this analysis, m will be assigned 50.

- *Analysis (Step 4)*. For each completed dataset use the model as it would have been applied had the data been complete for the continuous outcome. The final inference on treatment difference is conducted from the multiple datasets, as implemented in SAS[®] PROC MI ANALYZE.

The steps for this approach are detailed below:

1. Transpose data horizontally by study visit and impute all non-monotone (intermittent) missing data using the Markov Chain Monte Carlo (MCMC) method of PROC MI. Note that this imputation will sample data within each treatment group. SAS pseudo code is provided below.

```
PROC MI DATA=example seed = 6654 NIMPUTE = 20 OUT = outdata1;  
  BY <treatment>;  
  MCMC chain=multiple impute=monotone;  
  VAR <treatment> <baseline score> <visitX score> .. <visit6 score>;  
RUN;
```

2. Using the imputed datasets from Step #1 that are now monotone missing (no intermittent missing data), a single call to PROC MI (including the MNAR statement) will be utilized to impute the monotone missing data. Within the call to PROC MI, one timepoint is imputed at a time. When imputing at time-point t , the imputation step will include all vehicle subjects, but only those from the active arms that have a value missing at time-point t . Subjects with non-missing data that are on active arms will not contribute to the estimation for this step.

Repeat the above step for all timepoints t . Thus, the data for timepoint $t+1$ uses the data imputed from previous timepoints.

SAS pseudo code is provided below. SAS accomplishes this iterative process in one step.

```
PROC MI DATA=example seed = 2617 NIMPUTE = 1 OUT = outdata1;  
  BY __imputation__;  
  CLASS <treatment>;  
  MONOTONE REG ( / details);  
  MNAR MODEL (<v1 score> .. <v6 score> /  
    modelobs=(treatment=("vehicle")));  
  VAR <baseline score> <v1 score> .. <vX score>..<v6 score> ;  
RUN;
```

3. Pass the output from Step 2 into the model by the imputation variable (coalesce into one from each step above). When all missing data are imputed, PROC MIANALYZE will be used to combine the parameters from the analyses for inference.

8.2. Secondary Efficacy Analyses

8.2.1. Visual Index for Ichthyosis Severity (VIIS)

The investigator will rate the subject's condition using the 5-point VIIS for each body area (chest/abdomen, back, legs, and arms) and an overall score at all clinic visits. The scoring is as follows in [Table 5](#).

Table 5: VIIS Scoring Definitions

Score	Definition
0	Normal skin; no perceptible scale, or smoothening
1	Areas of normal skin intermixed with areas showing smoothening (diminished fine skin markings; shininess; waxiness) or small scales (visible separated/fractured stratum corneum)
2	Confluent smoothening (diminished fine skin markings; shininess; waxiness) or small scales (visible separated/fractured stratum corneum)
3	Confluent scales (visibly separated/fractured stratum corneum) including some large (>1cm), thick scales
4	Confluent, primarily large, thick scales

The change from baseline VIIS score will be analyzed using an MMRM. The MMRM model will include change from baseline in VIIS score as the dependent variable, treatment, study visit, treatment-by-visit interaction, and age group as fixed effects, subject as a random effect, and baseline VIIS score as a covariate. All post-baseline study visits will be included in the model; however, the primary comparison will be between the active trifarotene cream HE1 groups and vehicle at Day 90. An unstructured covariance matrix will be used to model the within-subject errors. The Kenward-Roger approximation will be used to estimate degrees of freedom. In case of convergence issues, other covariance structures will be explored including AR(1), CS, and VC with each model fit to find the covariance structure with the best fit. The fit statistics will be compared for all covariance structures; the structure with the smallest Akaike information criterion will be retained as the preferred model and noted in the resulting table. For the OLE period, the model will not include treatment or treatment-by-visit interaction since all subjects receive the same treatment in the OLE.

The LS mean change from baseline will be presented along with the associated 95% CI within each treatment group. The overall *P* value of the model will be presented to test the null hypothesis that the change from baseline to subsequent study visit is 0 with a 2-sided alternative considering a difference in either direction.

In comparing treatments (active trifarotene cream HE1 groups minus vehicle), LS mean differences in change from baseline will be presented along with associated 95% CIs and *P* values. The null hypothesis that the difference in change from baseline in active trifarotene cream HE1 groups minus control vehicle is 0 with a 2-sided alternative considering a difference in either direction.

The observed value and change from baseline in VIIS score will also be summarized descriptively by study visit and treatment group using descriptive statistics in addition to the above noted model for the Double-blind Period and OLE.

